No treatment-related deaths have been reported in any treatment cohort of Study CA011-001. Nine deaths were reported in participants treated with BMS-986158 monotherapy within 30 days of last dose. Of the 9 deaths, 8 deaths were reported as secondary to disease and 1 due to cerebrovascular accident; all of which were considered not related to BMS-986158 treatment.

A total of 68 subjects were discontinued from study treatment due to disease progression.

A detailed description of BMS-986158 safety is provided in the IB.

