- Duration of Response (DOR): defined for a subject with confirmed response as the time between the date of first response and the date of the first objectively documented disease progression (as determined by RECIST v1.1 for solid tumors, Lugano 2014 criteria for hematologic malignancies, or PCWG3 (including PSA assessments) for prostate cancer [CRPC or NEPC]), or death due to any cause, whichever occurs first. For those subjects who remain alive and have not progressed, duration of response will be censored on the date of last tumor assessment. Subjects who started subsequent therapy without a prior reported progression will be censored at the last tumor assessment prior to initiation of the subsequent anticancer therapy. Response duration will only be evaluated in subjects with a BOR of CR or PR.
- PFS: defined as the time from the first dose of study medication to the date of the first objective documentation of tumor progression or death due to any cause. Clinical deterioration in the absence of radiographic evidence is not considered progression for the purpose of determining PFS. Subjects who neither progressed nor died will be censored on the date of their last tumor assessment. Subjects who did not have any on-study tumor assessments will be censored on the date of the first dose of study medication. Subjects who started subsequent therapy without a prior reported progression will be censored at the last tumor assessment prior to initiation of the subsequent anticancer therapy.
- Progression Free Survival Rate (PFSR) at week 't' : defined as the proportion of subjects who remain progression free and surviving at 't' weeks (t=12, 24). The proportion will be calculated by the product-limit method (Kaplan-Meier estimate) which takes into account censored data.

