#### 4.2.1 Preliminary Antitumor Activity

Changes in solid tumor measurements and tumor response will be assessed by the RECIST v1.1 (Response Evaluation Criteria in Solid Tumors version 1.1) (Protocol Appendix 4), or PCWG3 for prostate cancer (Protocol Appendix 12). PCWG3 criteria is intended for Part 2 subjects and not Part 1 subjects. Changes in hematologic malignancies will be assessed using Lugano 2014 criteria (Protocol Appendix 9). In Schedule A (Part 1), tumor assessments will occur 8 weeks ( $\pm 1$  week) after treatment begins and continue every 8 weeks ( $\pm 1$  week) until investigator-assessed disease progression or treatment discontinuation. In Schedules B and C (Part 1), tumor assessments will occur 9 weeks ( $\pm 1$  week) after treatment begins and continue every 9 weeks ( $\pm 1$  week) until investigator-assessed disease progression or treatment discontinuation. In Part 2, Schedule A, tumor assessments will occur 8 weeks ( $\pm 1$  week) after treatment begins and continue every 8 ( $\pm 1$  week) until investigator-assessed disease progression or treatment discontinuation.

The following set of study-level efficacy endpoints will be used.

- Objective Response Rate (ORR): defined as the total number of subjects whose best overall response (BOR) is either a CR or PR divided by the total number of subjects in the population of interest.
  - Best overall response (BOR): defined as the best response designation recorded between the dates of first dose and the date of first objectively documented progression per Investigator assessed RECIST v1.1 (or Lugano 2014 criteria for hematologic malignancies or PCWG3 for prostate cancer) or the date of subsequent therapy, whichever occurs first.

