Investigator reported CR or PR was not always confirmed by a second scan. Therefore, ORR summaries will be presented regardless of confirmation. For subjects without documented progression or subsequent therapy, all available response designations will contribute to the BOR assessment. For subjects who continue treatment beyond progression or begin subsequent therapy, the BOR should be determined based on response designations recorded up to the time of the initial RECIST v1.1 (or by Lugano 2014 criteria for hematologic malignancies, or PCWG3 criteria for prostate cancer [CRPC or NEPC]) defined progression or subsequent therapy, whichever occurs first. For those subjects who have surgical resection, only pre-surgical tumor assessments will be considered in the determination of BOR.

- Duration of Response (DOR): defined as the time between the date of first response (CR or PR) and the date of the first objectively documented disease progression (as determined using RECIST v1.1 for solid tumors, Lugano 2014 criteria for hematologic malignancies, or PCWG3 (including PSA assessments) for prostate cancer [CRPC or NEPC]), or death due to any cause, whichever occurs first. For those subjects who remain alive and have not progressed, duration of response will be censored on the date of last evaluable tumor assessment. Subjects who started subsequent therapy without a prior reported progression will be censored at the last evaluable tumor assessment prior to initiation of the subsequent anticancer therapy. Response duration will only be evaluated in subjects with a BOR of CR or PR. Duration of response will be reported if there are more than 5 CR or PR in a tumor type
- Progression Free Survival (PFS): defined as the time from the first dose of study medication to the date of the first objective documentation of tumor progression or death due to any cause. Clinical deterioration in the absence of radiographic evidence is not considered progression for the purpose of determining PFS. Subjects who neither progressed nor died will be censored on the date of their last evaluable tumor assessment. Subjects who did not have any evaluable on-study tumor assessments will be censored on the date of the first dose of study medication. Subjects who started subsequent therapy without a prior reported progression will be censored at the last evaluable tumor assessment prior to initiation of the subsequent anticancer therapy.

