- Progression Free Survival Rate (PFSR) at week 't': defined as the proportion of subjects who remain progression free and surviving at 't' weeks (t=12, 24). The proportion will be calculated by the product-limit method (Kaplan-Meier estimate) which takes into account censored data.

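### The PFS rule for subjects with no evaluable scan has no exception for deaths, so it conflicts with the PFS event definition and, applied literally, would inflate PFS rates

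*SAP*

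**What the plan says.** SAP section 4.2.1 runs PFS from first dose "to the date of the first objective documentation of tumor progression or death due to any cause". Three censoring sentences matter here:

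- The general rule is limited to subjects without an event: "Subjects who neither progressed nor died will be censored on the date of their last evaluable tumor assessment".
- The next sentence has no such limit: "Subjects who did not have any evaluable on-study tumor assessments will be censored on the date of the first dose of study medication".
- The last one censors subjects who began subsequent therapy without a reported progression at their last evaluable assessment before that therapy.

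Protocol section 8.3.2.1 has the same structure and the same gap, without the word evaluable: "Subjects who did not have any on-study tumor assessments will be censored on the date of the first dose of study medication".

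On timing, the SAP states: "In Part 2, Schedule A, tumor assessments will occur 8 weeks" (plus or minus one week) after treatment begins. Part 1 Schedule A follows the same interval, and Part 1 Schedules B and C use 9 weeks. The PFS rates are Kaplan-Meier estimates at weeks 12 and 24. SAP section 7.5 bases the final efficacy analyses on the All Treated population, so subjects who die early are in the PFS analysis set.

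**The concern.** Two sentences in one bullet give opposite answers for the same subject. A patient who dies at week 5 with no scan is an event at week 5 by the definition, and is censored at day 0 by the no-scan sentence. No order of precedence is stated, so event status is left to whoever programs the endpoint.

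The case is foreseeable. The response-evaluable populations in protocol section 8.2 and SAP section 6.3 both provide for subjects who die without a post-baseline assessment. SAP section 4.2.1 also does not count clinical deterioration without radiographic evidence as progression. Before the first scheduled scan, then, death is often the only way an early failure can enter PFS. If the no-scan sentence prevails, the worst outcomes leave the risk set before the curve starts, which affects the PFS rates and possibly the median.

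The SAP's added word evaluable widens the gap slightly. Read literally, a subject whose only scans were not evaluable would be censored at day 0 however late the death occurred.

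**Working it through.** The plan states no PFS estimate or event count for this rule, so there is no figure to reproduce. The check compares the two treatments algebraically and then with numbers.

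**Inputs.** First scan at week 8 or 9 (SAP 4.2.1). Expansion cohorts of 5 to 9 (SAP 5.2). 81 subjects treated in Part 1 at the December 2018 cutoff (protocol 1.4.4). The number k who die before a first scan is not given; I assume 1 to 3 per cohort of nine and 1 to 9 of 81.

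**Formula.** Let k of N subjects die before any other event or censoring.

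- Deaths as events: after the k deaths the curve stands at (N-k)/N, and N-k subjects remain at risk.
- Deaths censored at day 0: the curve still stands at 1, with the same N-k subjects at risk.
- All later steps are identical, so literal rate / death-as-event rate = N/(N-k) at every later time.

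**Illustration at week 12.** Assumption: about half of the remaining subjects progress at the week-8 scan.

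| N | k | Still progression-free | Deaths as events | Literal rule | N/(N-k) |
|---|---|---|---|---|---|
| 9 | 1 | 4 | 4/9 = 0.444 | 4/8 = 0.500 | 1.125 |
| 9 | 2 | 3 | 3/9 = 0.333 | 3/7 = 0.429 | 1.286 |
| 9 | 3 | 3 | 3/9 = 0.333 | 3/6 = 0.500 | 1.500 |
| 81 | 1 | 40 | 40/81 = 0.494 | 40/80 = 0.500 | 1.012 |
| 81 | 5 | 38 | 38/81 = 0.469 | 38/76 = 0.500 | 1.066 |
| 81 | 9 | 36 | 36/81 = 0.444 | 36/72 = 0.500 | 1.125 |

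A product-limit calculation matched N/(N-k) in every scenario run. With k = 0 the two rules agree.

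**Median.** With 8-weekly scans the median moves in steps. In the scenarios run with early deaths it usually stayed at 8 weeks under both rules. With 4 deaths among 81 it moved from 8 weeks (rate 39/81 = 0.481, below one half) to 16 weeks (39/77 = 0.506, above one half; assuming 20% of the remainder progress at week 16).

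**Limit of the formula.** The ratio is exact only when the k deaths come before every other event or censoring. It does not apply exactly to a late death in a subject whose scans were all non-evaluable.

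**The case against.** The strongest reply is that the sentence is only a fallback date. The sentence before it restricts censoring to subjects with neither progression nor death and dates it at their last evaluable scan. The next sentence can be read as supplying a date for members of that group who have no such scan. On that reading no death is lost and the bias is zero. Other text points the same way: duration of response is censored only in subjects still alive and progression-free, and the week-12 and week-24 rates are defined by being progression-free and surviving. This reading stands as possible, so a reader who concludes that the plan certainly inflates PFS goes further than the text allows. It is not compelled, though. The subsequent-therapy sentence also lacks the alive condition, so the sentences read equally well as parallel rules.

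A reader might also take the safety summary, "Nine deaths were reported in participants treated with BMS-986158 monotherapy within 30 days of last dose", as an estimate of k: 9/81 = 11.1%. It is not one. Those deaths are counted from the last dose and may follow several cycles and scans. The entry criteria (life expectancy of at least 3 months, ECOG 0 to 1) should also limit deaths before week 8. The k = 9 row above is an extreme case, not an estimate.

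It is also true that PFS here is descriptive. There is no formal hypothesis, the two-stage boundaries use ORR only, and the SAP lists PFS and a death indicator for each treated participant, so a miscoded death could be found. Sampling error in one cohort is far larger than the shift from one death: at a rate of 60% with nine subjects, a normal approximation gives 1.96 x sqrt(0.6 x 0.4 / 9) = 0.32, or about 32 points either way. This limits the importance of the point but does not resolve the inconsistency.

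**Conclusion.** The point holds as an internal inconsistency in SAP section 4.2.1, repeated in protocol section 8.3.2.1. The plan does not determine whether a death without an evaluable scan is a PFS event. The consequence depends on two things the documents leave open: which sentence prevails, and how many such deaths occur.

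If the no-scan sentence is applied literally and k such deaths come first, PFS rates rise by the factor N/(N-k): 12.5% relative for one of nine, 28.6% for two of nine, and 1.2% for one of 81. If the sentence is read as part of the preceding rule, or if k = 0, there is no effect. Certain inflation, or an 11% early-death share, is not supported.

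No error rate, sample size or decision boundary changes. Censoring living subjects with no scan at first dose is not in question.

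**What to change.** Replace the single no-scan sentence in SAP section 4.2.1 with three cases for subjects who have no evaluable on-study tumor assessment:

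1. Did not die: censored on the date of first dose.
2. Died without having started subsequent anticancer therapy: event on the date of death.
3. Started subsequent anticancer therapy before death: censored on the date of first dose, in line with the existing subsequent-therapy rule.

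The third case is needed because a bare statement that all deaths are events would create a new conflict with the subsequent-therapy sentence, which gives no usable date when there is no prior evaluable scan.

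The cost is a short SAP edit and the matching derivation in the PFS program. No new data are needed. The protocol need not be amended for this: SAP section 1 says the SAP supersedes the protocol's statistical considerations and that substantial differences will be identified, so a line noting the clarification against protocol section 8.3.2.1 is enough. If the sponsor already intends deaths to count, the edit merely records that.

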#### **4.2.2 Pharmacokinetic Endpoints**

Pharmacokinetics of BMS-986158 monotherapy (parent and metabolite, as data permits) will be derived from plasma concentrations versus time data.

Throughout the SAP, TAU was replaced by 24 hours or 0-24. This is because it is more meaningful to compare PK of first 24 hours following single dose kinetics on cycle 1 day 1, and the dosing interval of 24 hours on cycle 2 NCA (Cycle 2 Day 5 for schedule A, Cycle 2 Day 14 for schedule B and Cycle 2 Day 7 for schedule C). Therefore, with reference to the protocol, the following PK parameters were replaced in the SAP: Ctau was replaced by C24, AUC(TAU) was replaced by AUC(0-24), AI\_AUC(Tau) was replaced by AI\_AUC(0-24), AI\_Ctau was replaced by AI\_C24 and MR\_AUC(TAU) was replaced by MR\_AUC(0-24).

The PK parameters to be assessed following single and multiple dose administration are shown in Tables 4.2.2-1 through 4.2.2-4 below.

**Table 4.2.2-1: Single Dose Pharmacokinetic Endpoints**

Parameter	Definition
C max	Maximum observed plasma concentration
T max	Time of maximum observed plasma concentration
AUC(0-T)	Area under the plasma concentration-time curve from time zero to time of last quantifiable concentration
AUC(0-24)	Area under the concentration-time curve from time zero to time 24 hours
C max /D	Maximum observed plasma concentration; Dose normalized
AUC(0-24)/D	Area under the concentration-time curve from time zero to time 24 hours; Dose normalized
AUC(INF)/D	Area under the plasma concentration-time curve from time zero extrapolated to infinite time; Dose normalized

In addition, the following PK parameters may also be assessed after single dose administrations, if data permit:

**Table 4.2.2-2: Extended Single and Multi-dose Pharmacokinetic Endpoints**

Parameter	Definition
T-HALF	Apparent terminal phase half-life
AUC(INF)	Area under the plasma concentration-time curve from time zero extrapolated to infinite time
CLT/F	Apparent total body clearance, reported only for parent, not for metabolite
V z /F	Apparent volume of distribution of terminal phase, reported only for parent, not for metabolite

The PK parameters to be assessed following multiple dose administration include:

**Table 4.2.2-3: Multi-dose Pharmacokinetic Endpoints**

Parameter	Definition
C max	Maximum observed plasma concentration
T max	Time of maximum observed plasma concentration
AUC(0-T)	Area under the plasma concentration-time curve from time zero to time of last quantifiable concentration
AUC(0-24)	Area under the concentration-time curve from time zero to time 24 hours
C min	The minimum observed concentration within a dosing interval
C 24	Observed concentration at 24 hours
C trough	Trough observed plasma concentration (this includes predose concentrations (C 0 ) and concentrations at the end of dosing interval (C 24 ));

**Table 4.2.2-3: Multi-dose Pharmacokinetic Endpoints**

AI_AUC(0-24)	Accumulation Index; ratio of an exposure measure at steady-state to that after the first dose (exposure measure includes AUC(0-24)).
AI_Cmax	Accumulation Index; ratio of Cmax at steady-state to Cmax after the first dose
AI_C24	Accumulation Index; ratio of an C24 at steady-state to C24 after the first dose
T-HALFeff	Effective elimination half-life that explains the degree of accumulation observed for a specific exposure measure

In addition, the following PK parameters may also be assessed after single and multiple dose administrations, if data permit:

[figure not shown]
**Table 4.2.2-4: Extended Single and Multi-dose Pharmacokinetic Endpoints**

Parameter	Definition
MR_Cmax	Ratio of metabolite Cmax to parent Cmax, corrected for molecular weight
MR_AUC(0-T)	Ratio of metabolite AUC(0-T) to parent AUC(0-T), corrected for molecular weight
MR_AUC(INF)	Ratio of metabolite AUC(INF) to parent AUC(INF), corrected for molecular weight (following single dose only)
MR_AUC(0-24)	Ratio of metabolite AUC(0-24) to parent AUC(0-24), corrected for molecular weight

Individual subject pharmacokinetic parameter values will be derived by non-compartmental methods by a validated pharmacokinetic program. Actual times will be used for the analyses.

### 4.2.3 ECG/QTc

Changes in QTcF ( $\Delta$ QTcF) from baseline, at selected times in relation to BMS-986158 monotherapy will be evaluated in the context of dose- or exposure-response as observed. This may also be evaluated in relation to Metabolite BMT-161485.

## **5 SAMPLE SIZE AND POWER**

### **5.1 Dose Escalation**

In the dose escalation part of the study, i.e., Part 1, the sample size per dose level and schedule cannot be precisely determined but depends on the observed DLT and the decision rule of mTPI. Between 3 and up to 13 DLT evaluable subjects may be enrolled to a given dose level and schedule. Treating additional subjects beyond the 13 at a dose level in a dose schedule would be unlikely to alter the decision specified by the mTPI algorithm. A total of approximately 30 subjects is expected to be treated per schedule, with a total of 90 planned across schedules for the dose escalation phase. More subjects may be added at a specific schedule if additional dose levels need to be evaluated. Similarly, fewer than 30 subjects may be needed for a different schedule if a smaller number of dose levels are evaluated.

Assuming a 27% acceptable DLT rate, which corresponds to a Beta(1, 2.7) distribution, the risk associated with selecting a dose level as safe given the number of DLTs observed at that dose level based on the posterior probability associated with an observed DLT is dependent on the number of subjects evaluable for DLT at that dose level at the time of the event.

### **5.2 Dose-expansion Cohort**

The purpose of cohort expansion is to gather additional safety, tolerability, preliminary efficacy, PK, [REDACTED] information regarding BMS-986158 alone. However, the sample size is strictly based on efficacy, specifically based on the target ORR relative to historic response rate.

During this part of the study, the efficacy signal assessment in each tumor cohort in monotherapy regimens will be guided by a Fleming 2-stage design. The Stage 1 and total (Stages 1 and 2) sample size for each cohort is calculated based on assumptions of true (target) and historic ORR for each tumor type in the studied population. Using a 2-stage design provides an option to stop early for futility, as well as an early signal of preliminary strong antitumor activity. Approximately 5 to 9 subjects will be treated in each of the 5 parallel cohorts. Enrollment may continue during the initial

Stage 1 efficacy evaluation (while the planned number of participants for Stage 1 are followed for evaluable tumor assessments) to ensure that sufficient subjects are response evaluable in case of early drop outs and to account for design parameters changes (eg, historical rate update).

The total sample size for each expansion cohort will be calculated to provide a reasonable false-positive rate (FPR < 10%) and false-negative rate (FNR < 10%) based on assumptions of true (target) and historic ORR for each indication. The assumed historic and target response rates may change over time and may need to be adjusted by the time of response data from this study are available. Enrollment may continue into stage 2 while the planned number of participants for stage 1 are followed for efficacy evaluable tumor assessments. There will be no stopping of a disease cohort for efficacy, although early planning for the next stage of clinical development may be initiated.

If one or more of the 5 subjects in a Stage 1 cohort respond to therapy, the Fleming Stage 1 futility boundary will have been exceeded and enrollment will continue in Stage 2. If 2 or fewer of 9 subjects enrolled through Stage 2 respond to therapy, the cohort will have failed to evidence the targeted ORR (Table 5.2-1).

**Table 5.2-1: Characteristics for Initial Monotherapy Expansion Cohorts Signal assessment when guided by a Two-Stage Design**

Tumor Cohort and Group	Target ORR %	SOC ORR %	Stage 1 / Total N	Stage 1 Res Futility/ Efficacy Boundary	Stage 2 Res Futility/ Efficacy Boundary	FPR/FNR (%)
FUSION PROTEINS						
NMC	50	10	5/9	0/2	2/3	10/10
DHL	50	10	5/9	0/2	2/3	10/10
BRD AMPLIFICATIONS						
TNBC	50	10	5/9	0/2	2/3	10/10
MYC AMPLIFICATIONS						
Non-GC-DLBCL	35	10	5/9	0/2	1/2	20/20
AR AMPLIFICATIONS						
CRPC	35	10	5/9	0/2	1/2	20/20

Abbreviations: CRPC = castrate-resistant prostate cancer; DHL = double-hit lymphoma; FNR = false negative rate; FPR = false positive rate; N = number of subjects; NMC = NUT-midline carcinoma; ORR = objective response rate; RCC = renal cell carcinoma; Res = response; SOC = standard of care; TNBC = triple negative breast cancer; Non-GC-DLBCL = Non-germinal center diffuse large B-cell lymphoma;

The planned sample size consists of up to approximately 90 subjects for Part 1 and up to approximately 45 subjects for Part 2 Initial expansion for a total of up to approximately 135 subjects in the entire study (up to Part 2 Initial expansion, as clarified in the scope of this SAP document in the beginning).

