### Schedule of Analyses:

Data emerging from this study may be needed to for timely decisions about adjustments to procedures in subsequent parts of the study. Therefore, data from each part of the study will be examined prior to the final lock of the study database. Additional interim analyses may also be performed for administrative purposes, early termination of the study or publications. No formal inferences requiring any adjustment to statistical significance level will be performed. Efficacy analyses based on interim data may use the Response Evaluable Subjects population or the All Treated Subjects population depending on the purpose of the analysis.

An interim analysis to summarize safety, PK, and efficacy data may be performed when sufficiently treated participants become available. Additional interim analyses on safety and efficacy may be performed at various times prior to study completion in order to facilitate program decisions and to support scientific publications or presentations.

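### SAP 5.2 allows the historic and target ORR to be adjusted without requiring that the change precede a cohort's responses or rest on external data, so the stated error rates of the Fleming boundaries are not secured

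*SAP*

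**What the plan says.** SAP Section 5.2 states that "the sample size is strictly based on efficacy, specifically based on the target ORR relative to historic response rate". It then says of these inputs: "historic and target response rates may change over time and may need to be adjusted by the time of response data from this study". The same section lets enrollment continue during the Stage 1 evaluation, partly "to account for design parameters changes (eg, historical rate update").

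Table 5.2-1 gives target ORR, historic ORR, Stage 1 and total N, the two pairs of boundaries, and FPR/FNR:

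- "NMC 50 10 5/9 0/2 2/3 10/10", with the same values for DHL and TNBC.
- "CRPC 35 10 5/9 0/2 1/2 20/20", with the same values for non-GC-DLBCL.

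Protocol Section 8.1 (Table 8.1-2) has the same rates and boundaries and no adjustment clause.

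The study is open-label (SAP 2.3). Under Schedule of Analyses in SAP Section 1, "data from each part of the study will be examined prior to the final lock of the study database". Protocol Section 7 lists a data monitoring committee as not applicable.

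**The concern.** The pass mark follows from two inputs, the historic and the target ORR. The SAP allows both to change and ties the change only loosely to the arrival of response data. It names no decision maker and no evidence standard. It does not require the change to be made without reference to the cohort's own responses.

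A false-positive or false-negative rate describes a rule chosen before the data. If the mark for a cohort of nine is settled once two responders are known, the FPR and FNR columns no longer describe what was done.

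No hypothesis test is at stake. What is at stake is how a small cohort is read. Protocol Section 3.1 ties Subsequent Expansion, of up to 126 subjects, to signals of antitumor activity or favorable pharmacodynamic effects in the Initial Expansion. Readers will set the ORR of each cohort beside the error rates in the table.

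**Working it through.** **Inputs (SAP 5.2 and Table 5.2-1).** Stage 1 n = 5, total n = 9, futility at 0 of 5, no stopping for efficacy. Final mark: at least 3 of 9 in the 50%-target cohorts and at least 2 of 9 in the 35%-target cohorts. Historic ORR is 10% throughout.

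**Formula.** With X responders among the first 5 and Y among the next 4, and final mark r:

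P(signal) = Σ over x = 1 to 5 of P(X = x) × P(Y ≥ r − x)

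**At true ORR 10%.** P(X=1) = 0.32805, P(X=2) = 0.07290, P(X≥3) = 0.00856, P(Y≥1) = 0.3439, P(Y≥2) = 0.0523.

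- r = 3: 0.32805 × 0.0523 + 0.07290 × 0.3439 + 0.00856 = 0.0508.
- r = 2: 0.32805 × 0.3439 + 0.07290 + 0.00856 = 0.1943.

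**The plan's own figures, reproduced as nominal upper limits.**

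| Design | Stage 1 efficacy boundary | FPR | FNR | Stated |
|---|---|---|---|---|
| 50 vs 10, mark 3 of 9 | not used | 5.1% | 10.0% | 10/10 |
| 50 vs 10, mark 3 of 9 | 2 of 5 counts as a signal | 9.9% | 8.0% | 10/10 |
| 35 vs 10, mark 2 of 9 | either | 19.4% | 17.2% | 20/20 |

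The table's arithmetic is sound. The missing part is the lock.

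**Mark lowered by one responder in a 50%-target cohort, true ORR 10%.**

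- One cohort: 5.1% becomes 19.4%, about fourfold.
- At least one false signal in three such cohorts, taken as independent: 1 − (1 − 0.0508)³ = 14.5% becomes 1 − (1 − 0.1943)³ = 47.7%.
- If 2 of 5 in Stage 1 already counts as a signal, the starting point is 9.9% per cohort and 1 − (1 − 0.0986)³ = 26.8% across three. The end points are unchanged, so the rise is about twofold.

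**If the mark is lowered only sometimes.** The difference, 19.4% − 5.1% = 14.3%, is the chance of passing Stage 1 futility and ending with exactly 2 of 9. If the mark drops on a fraction q of those occasions, FPR = 5.1% + q × 14.3%. It exceeds the stated 10% once q is above about (10 − 5.1)/14.3 = 0.34.

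**Mark raised by one responder in a 35%-target cohort, true ORR 35%.** P(X=1) = 0.3124, P(X=2) = 0.3364, P(X≥3) = 0.2352, P(Y≥1) = 0.8215, P(Y≥2) = 0.4370.

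- r = 2: 0.3124 × 0.8215 + 0.3364 + 0.2352 = 82.8%.
- r = 3: 0.3124 × 0.4370 + 0.3364 × 0.8215 + 0.2352 = 64.8%. This is 70.8% if 2 of 5 in Stage 1 counts as a signal.

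**Could a modest benchmark change move the mark?** The documents give no revised rates, so these are assumptions (no efficacy stop). With a historic rate of 5%, 2 of 9 has a calculated FPR of 6.0% and would look acceptable. With 15%, 3 of 9 has 13.6%, above the stated 10%. A five-point change either way is enough to shift the mark.

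**The case against.** The strongest reply is that the boundaries carry little weight. The SAP states no formal hypothesis, the Fleming design only guides the assessment, nothing stops for efficacy, and SAP 2.1 leaves cohort decisions to the Sponsor/Medical Monitor on a comprehensive assessment. ORR is also reported by tumor type with Clopper-Pearson limits that depend on no boundary, so any reader can compare the count with the printed mark. SAP Section 1 promises to identify substantial differences from the protocol. All of this stands and limits the harm. It does not stop a mark being changed after responses are known, or restore the meaning of the FPR and FNR if it is.

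Several stronger readings are tempting but not supported:

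- A reader might infer that the boundaries are the only decision rule for the cohorts. They are not: decisions rest on the totality of evidence.
- A reader might infer that the SAP plans to reset the mark after seeing responses. The wording can equally mean an update completed before the data arrive. The documents permit a later change; they do not announce one.
- A reader might infer continuous sponsor review. The SAP says only that data from each part are examined before final lock and that further interim analyses may be done.
- A reader might use a single-stage binomial with n = 9, giving 22.5% for 2 of 9 at a true 10%. That ignores the Stage 1 futility rule and overstates the figure.
- A reader might see the historical-rate clause as a second licence to move the mark. It concerns continued enrollment during Stage 1, not the boundary.

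The 47.7% is also an unfavorable case: all three cohorts loosened together with the true rate at 10% in each. The 19.4% per cohort lies within the 20% the plan already accepts for CRPC and non-GC-DLBCL. It still exceeds the 10% stated for the cohorts in question.

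**Conclusion.** The point holds as a gap in pre-specification. The SAP permits the two inputs behind the boundaries to change and does not require the change to come before the cohort's responses, to use external data, or to be shown beside the printed boundaries. One responder's movement takes the false-positive rate of a 50%-target cohort from 5.1% to 19.4%, or from 9.9% if 2 of 5 in Stage 1 already counts as a signal. In the other direction, it takes the chance of a signal in a 35%-target cohort from 82.8% to 64.8%.

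These figures assume the futility stop at 0 of 5 is applied, true rates of 10% and 35% respectively, and, for the three-cohort figure, independence. They show what a shift would do; the documents do not show that one has occurred. The consequence is for reading the signal and planning later cohorts. The safety objectives and the reported ORR estimates are unaffected.

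**What to change.** In SAP 5.2, replace the sentence on changing response rates with:

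> The rates and boundaries in Table 5.2-1 are fixed before the first post-baseline tumor assessment in each cohort. Any later update will rest only on external data, be dated in a SAP amendment, and be reported next to the result against the original boundary.

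If responses have already been seen in a cohort, report that cohort against the Table 5.2-1 boundary in any case. The enrollment clause that mentions a historical rate update can stay.

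The lock should name the table, because the text of the same section gives a single mark for every cohort ("If 2 or fewer of 9 subjects enrolled through Stage 2 respond to therapy, the cohort will have failed to evidence the targeted ORR"), while the table fails the 35%-target cohorts only at 1 or fewer. Until the two agree, 2 of 9 in CRPC or non-GC-DLBCL passes by the table and fails by the text.

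The cost is SAP wording only, with no effect on conduct or sample size. The downside is slightly less flexibility if outside benchmarks change during the study. Reporting against both boundaries meets most of that.
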